Table 14.3.4.1.2 Shift from Baseline for Hematology Parameters (Safety Population)

Early Termination

Repeat for all

Hematology parameters Repeat for Vehicle

[1] Percentage and all subsequent percentages based on the number treated.

[2] Parameters with reference range indicators equal to High or Low are counted as Abnormal.

Source: Listing XXXX

PROGRAM NAME: XXXXXXXXXX

DATE: HH:MM/DDMMMYYYY

- Repeat for 14.3.4.2.2 Shift from Baseline for Chemistry Parameters for Safety Population
- Repeat for 14.3.4.3.2 Shift from Baseline for Urinalysis Parameters for Safety Population

| | | B244 O.D. 5.0 | B244 O.D. 20.0 | Pooled B244 | Vehicle |
|---|----------------|---------------|----------------|--------------|--------------|
| | Statistic | (N=xx) | (N=xx) | (N=xx) | (N=xx) |
| Total Weight Dispensed (g) | n | XX | XX | XX | XX |
| | Mean (SD) | xx.x (xx.xx) | xx.x (xx.xx) | xx.x (xx.xx) | xx.x (xx.xx) |
| | Median | XX.X | XX.X | XX.X | XX.X |
| | Min, Max | XX, XX | XX, XX | XX, XX | XX, XX |
| Total Weight Returned (g) | n | XX | XX | XX | XX |
| | Mean (SD) | xx.x (xx.xx) | xx.x (xx.xx) | xx.x (xx.xx) | xx.x (xx.xx) |
| | Median | XX.X | XX.X | XX.X | XX.X |
| | Min, Max | XX, XX | XX, XX | XX, XX | XX, XX |
| Net Weight of Study Drug (g) [1] | n | XX | XX | XX | XX |
| | Mean (SD) | xx.x (xx.xx) | xx.x (xx.xx) | xx.x (xx.xx) | xx.x (xx.xx) |
| | Median | XX.X | XX.X | XX.X | XX.X |
| | Min, Max | XX, XX | XX, XX | XX, XX | XX, XX |
| Compliance (%) based on IP Weight [2] | n | XX | XX | XX | XX |
| | Mean (SD) | xx.x (xx.xx) | xx.x (xx.xx) | xx.x (xx.xx) | xx.x (xx.xx) |
| | Median | XX.X | XX.X | XX.X | XX.X |
| | Min, Max | XX, XX | XX, XX | XX, XX | XX, XX |
| 50% IP Applied [3] | | | | | |
| Yes | n (%) | xx (xx.x) | xx (xx.x) | xx (xx.x) | xx (xx.x) |
| No | n (%) | xx (xx.x) | xx (xx.x) | xx (xx.x) | xx (xx.x) |
| Number of Dosing Diaries Entered [4] | n | XX | XX | XX | XX |
| | Mean (SD) | xx.x (xx.xx) | xx.x (xx.xx) | xx.x (xx.xx) | xx.x (xx.xx) |
| | Median | XX.X | XX.X | XX.X | XX.X |
| | Min, Max | XX, XX | XX, XX | XX, XX | XX, XX |
| | | | | | |
| Compliance (%) based on Diary Entries [5] | n Mara (CD) | XX | XX | XX | XX |
| | Mean (SD) | XX.X (XX.XX) | XX.X (XX.XX) | XX.X (XX.XX) | XX.X (XX.XX) |
| | Median | XX.X | XX.X | XX.X | XX.X |
| | Min, Max | XX, XX | XX, XX | XX, XX | XX, XX |

Table 14.3.5 Summary of Drug Accountability and Compliance at End of Week 4 (Safety Population)

[1] Net Weight of Study Drug (g) = (Total Weight Dispensed (g)) – (Total Weight Returned (g)).
 [2] Compliance (%) based on IP Weight = (Net Weight of Study Drug (g)) / (Planned Study Drug Use per Day (g) * Number of Days Expected Use of Study Drug) where Planned Study Drug Used per Day = 2.8g and Number of Days Expected Use of Study Drug = 28 days.

[3] Subjects who administered at least 50% of IP (where Net Weight of Study Drug (g) is at least 50% of the initial product weight (g) (i.e., 0.14 g per pump * 20 pumps per day * 28 days = 78.4 g).

[4] Number of Dosing Diaries Entered = Number of dosing diaries entered with a YES confirming study drug dosing.

[5] Compliance (%) based on Diary Entries = (Number of Dosing Diaries Entered) / (Number of Dosing Diaries Available) where Number of Dosing Diaries Available is the total number of dosing diaries expected from a 28 day treatment (56 diaries).

Source: Listing XXXX

PROGRAM NAME: XXXXXXXXXX
| | | | B244 O.D. 5.0 | B244 O.D. 20.0 | Pooled B244 | Vehicle |
|--------------------------------------|-----------------------|-----------|---------------|----------------|--------------|--------------|
| Local Tolerability Symptom | Day | Statistic | (N=xx) | (N=xx) | (N=xx) | (N=xx) |
| Skin Redness and/or Color Change | Day 1 | n | XX | XX | XX | XX |
| | | Mean (SD) | xx.x (xx.xx) | xx.x (xx.xx) | xx.x (xx.xx) | xx.x (xx.xx) |
| | | Median | XX.X | XX.X | XX.X | XX.X |
| | | Min, Max | XX, XX | XX, XX | xx, xx | XX, XX |
| | Day 2 | n | XX | XX | XX | XX |
| | | Mean (SD) | xx.x (xx.xx) | xx.x (xx.xx) | xx.x (xx.xx) | xx.x (xx.xx) |
| | | Median | XX.X | XX.X | XX.X | XX.X |
| | | Min, Max | XX, XX | XX, XX | XX, XX | XX, XX |
| | Day 2 CFPD | n | XX | XX | XX | XX |
| | | Mean (SD) | xx.x (xx.xx) | xx.x (xx.xx) | xx.x (xx.xx) | xx.x (xx.xx) |
| | | Median | XX.X | XX.X | XX.X | XX.X |
| | | Min, Max | XX, XX | XX, XX | XX, XX | XX, XX |
| | Day 3 | n | XX | XX | XX | XX |
| | | Mean (SD) | xx.x (xx.xx) | xx.x (xx.xx) | xx.x (xx.xx) | xx.x (xx.xx) |
| | | Median | XX.X | XX.X | XX.X | XX.X |
| | | Min, Max | XX, XX | XX, XX | xx, xx | xx, xx |
| | Day 3 CFPD | n | XX | XX | XX | XX |
| | | Mean (SD) | xx.x (xx.xx) | xx.x (xx.xx) | xx.x (xx.xx) | xx.x (xx.xx) |
| | | Median | XX.X | XX.X | XX.X | XX.X |
| | | Min, Max | XX, XX | XX, XX | XX, XX | XX, XX |
| | Day 4 | n | XX | XX | XX | XX |
| | - | Mean (SD) | xx.x (xx.xx) | xx.x (xx.xx) | xx.x (xx.xx) | xx.x (xx.xx) |
| | | Median | XX.X | XX.X | XX.X | XX.X |
| | | Min, Max | XX, XX | XX, XX | XX, XX | XX, XX |
| | Day 4 CFPD | n | XX | XX | XX | XX |
| | - | Mean (SD) | xx.x (xx.xx) | xx.x (xx.xx) | xx.x (xx.xx) | xx.x (xx.xx) |
| | | Median | XX.X | XX.X | XX.X | XX.X |
| Repeat for all Patient Reported | | Min, Max | XX, XX | XX, XX | XX, XX | XX, XX |
| Local Tolerability Symptoms | Repeat for Days 5 – 7 | • | | - | · | |
| [1] CEDD - Change from Dravieus Dave | | | | | | |

Table 14.3.6.1 Summary of Values and Change from Previous Day for Patient Reported Local Tolerability (Safety Population)

[1] CFPD = Change from Previous Day. Source: Listing XXXX PROGRAM NAME: XXXXXXXXXX

| | | | | | | Previous Da | ay Value | |
|--------------------|---------------|------------|-----------------|-----------|-----------|-------------|-----------|-----------|
| Local Tolerability | Treatment | | | | | | | |
| Symptom | Group | Day | Day 2 – 7 Value | Statistic | None | Mild | Moderate | Severe |
| Skin Redness | B244 O.D. 5.0 | Day 2 | None | n (%) | xx (xx.x) | xx (xx.x) | xx (xx.x) | xx (xx.x) |
| and/or Color | (N=xx) | | Mild | n (%) | xx (xx.x) | xx (xx.x) | xx (xx.x) | xx (xx.x) |
| Change [1] | | | Moderate | n (%) | xx (xx.x) | xx (xx.x) | xx (xx.x) | xx (xx.x) |
| | | | Severe | n (%) | xx (xx.x) | xx (xx.x) | xx (xx.x) | xx (xx.x) |
| | | Day 3 | None | n (%) | xx (xx.x) | xx (xx.x) | xx (xx.x) | xx (xx.x) |
| | | 2 | Mild | n (%) | xx (xx.x) | xx (xx.x) | xx (xx.x) | xx (xx.x) |
| | | | Moderate | n (%) | xx (xx.x) | xx (xx.x) | xx (xx.x) | xx (xx.x) |
| | | | Severe | n (%) | xx (xx.x) | xx (xx.x) | xx (xx.x) | xx (xx.x) |
| | | Day 4 | None | n (%) | xx (xx.x) | xx (xx.x) | xx (xx.x) | xx (xx.x) |
| | | - | Mild | n (%) | xx (xx.x) | xx (xx.x) | xx (xx.x) | xx (xx.x) |
| | | | Moderate | n (%) | xx (xx.x) | xx (xx.x) | xx (xx.x) | xx (xx.x) |
| | | | Severe | n (%) | xx (xx.x) | xx (xx.x) | xx (xx.x) | xx (xx.x) |
| | Repeat for | | | | | | | |
| Repeat for all | B244 O.D. | Day 5 | None | n (%) | xx (xx.x) | xx (xx.x) | xx (xx.x) | xx (xx.x) |
| Patient Reported | 20.0, Pooled | | Mild | n (%) | xx (xx.x) | xx (xx.x) | xx (xx.x) | xx (xx.x) |
| Local Tolerability | B244, and | Repeat for | Moderate | n (%) | xx (xx.x) | xx (xx.x) | xx (xx.x) | xx (xx.x) |
| Symptoms | Vehicle | Days 6, 7 | Severe | n (%) | xx (xx.x) | xx (xx.x) | xx (xx.x) | xx (xx.x) |
| | | | | | | | | |

Table 14.3.6.2 Shift from Previous Day for Patient Reported Local Tolerability (Safety Population)

[1] Percentage and all subsequent percentages based on the number treated. Source: Listing XXXX PROGRAM NAME: XXXXXXXXXX

| | | | B244 O.D. 5.0 | B244 O.D. 20.0 | Pooled B244 | Vehicle |
|---|--|-------------|---------------|----------------|--------------|--------------|
| Vital Signs | Visit | Statistic | (N=xx) | (N=xx) | (N=xx) | (N=xx) |
| Diastolic Blood Pressure (mmHg) | Screening | n | XX | XX | XX | XX |
| | | Mean (SD) | xx.x (xx.xx) | xx.x (xx.xx) | xx.x (xx.xx) | xx.x (xx.xx) |
| | | Median | XX.X | XX.X | XX.X | XX.X |
| | | Min, Max | XX, XX | XX, XX | XX, XX | XX, XX |
| | Baseline | n | XX | XX | XX | XX |
| | | Mean (SD) | xx.x (xx.xx) | xx.x (xx.xx) | xx.x (xx.xx) | xx.x (xx.xx) |
| | | Median | XX.X | XX.X | XX.X | XX.X |
| | | Min, Max | XX, XX | XX, XX | XX, XX | XX, XX |
| | Week 2 | n M (CD) | xx | xx | xx | xx |
| | | Mean (SD) | XX.X (XX.XX) | XX.X (XX.XX) | XX.X (XX.XX) | XX.X (XX.XX) |
| | | Median | XX.X | XX.X | XX.X | XX.X |
| | | Min, Max | XX, XX | XX, XX | XX, XX | XX, XX |
| | Week 2 CFB [1] | n | XX | XX | XX | XX |
| | | Mean (SD) | xx.x (xx.xx) | xx.x (xx.xx) | xx.x (xx.xx) | xx.x (xx.xx) |
| | | Median | XX.X | XX.X | XX.X | XX.X |
| | | Min, Max | XX, XX | XX, XX | XX, XX | XX, XX |
| | Week 4 | n | XX | XX | XX | XX |
| | | Mean (SD) | xx.x (xx.xx) | xx.x (xx.xx) | xx.x (xx.xx) | xx.x (xx.xx) |
| | | Median | XX.X | XX.X | XX.X | XX.X |
| | | Min, Max | XX, XX | XX, XX | xx, xx | xx, xx |
| | Week 4 CFB | n | XX | XX | XX | XX |
| | | Mean (SD) | xx.x (xx.xx) | xx.x (xx.xx) | xx.x (xx.xx) | xx.x (xx.xx) |
| Repeat for Systolic Blood Pressure, | | Median | XX.X | XX.X | xx.x | XX.X |
| Heart Rate, Respiratory Rate, and Temperature | Repeat for Week 8 and Early Termination | Min, Max | XX, XX | xx, xx | XX, XX | xx, xx |

Table 14.3.7 Summary of Values and Change from Baseline for Vital Signs (Safety Population)

[1] CFB = Change from Baseline. Source: Listing XXXX PROGRAM NAME: XXXXXXXXXX

Programming Note:

• Height, Weight, BMI, and BSA are reported in table 14.1.3.1 and should not be included here.

Table 14.3.8.1 Summary of Prior Medications by ATC Class Level 1 and Preferred Term (Safety Population)

| | | B244 O.D. 5.0 | B244 O.D. 20.0 | Pooled B244 | Vehicle |
|---|-----------|---------------|----------------|-------------|-----------|
| | Statistic | (N=xx) | (N=xx) | (N=xx) | (N=xx) |
| Number of Subjects with at Least One Prior Medication [1] | n (%) | xx (xx.x) | xx (xx.x) | xx (xx.x) | xx (xx.x) |
| ATC Class Level 1 #1 [2,3] | n (%) | xx (xx.x) | xx (xx.x) | xx (xx.x) | xx (xx.x) |
| Preferred Term #1 | n (%) | xx (xx.x) | xx (xx.x) | xx (xx.x) | xx (xx.x) |
| Preferred Term #2 | n (%) | xx (xx.x) | xx (xx.x) | xx (xx.x) | xx (xx.x) |
| Preferred Term #3 | n (%) | xx (xx.x) | xx (xx.x) | xx (xx.x) | xx (xx.x) |
| etc. | | | | | |
| ATC Class Level 1 #2 | n (%) | xx (xx.x) | xx (xx.x) | xx (xx.x) | xx (xx.x) |
| Preferred Term #1 | n (%) | xx (xx.x) | xx (xx.x) | xx (xx.x) | xx (xx.x) |
| Preferred Term #2 | n (%) | xx (xx.x) | xx (xx.x) | xx (xx.x) | xx (xx.x) |
| Preferred Term #3 | n (%) | xx (xx.x) | xx (xx.x) | xx (xx.x) | xx (xx.x) |
| etc. | | | | | |

[1] Percentage and all subsequent percentages based on the number treated.
[2] Subjects will be counted once per ATC Class/Preferred Term.
[3] WHO Drug Dictionary version YYYYMMM was used to code medication names.

Source: Listing XXXX PROGRAM NAME: XXXXXXXXXX

DATE: HH:MM/DDMMMYYYY

Programming Note:

• Repeat for 14.3.8.2 Summary of Concomitant Medications by ATC Class Level 1 and Preferred Term for Safety Population

Table 14.3.8.3 Summary of Rescue Medications by Class (Safety Population)

| | Statistic | B244 O.D. 5.0 | B244 O.D. 20.0 | Pooled B244 | Vehicle |
|--|------------------|--|--------------------------------------|--|--|
| | Statistic | | (IN=XX) | (IN=XX) | (IN=XX) |
| Number of Subjects with at Least One Rescue Medication [1] | n (%) | xx (xx.x) | xx (xx.x) | xx (xx.x) | xx (xx.x) |
| Class 4: Mid-Strength [2] | | | | | |
| Clocortolone pivalate (0.1%) | n (%) | xx (xx.x) | xx (xx.x) | xx (xx.x) | xx (xx.x) |
| Mometasone furoate (0.1%) | n (%) | xx (xx.x) | xx (xx.x) | xx (xx.x) | xx (xx.x) |
| Triamcinolone acetonide (0.1%) | n (%) | xx (xx.x) | xx (xx.x) | xx (xx.x) | xx (xx.x) |
| Betamethasone valerate (0.1%) | n (%) | xx (xx.x) | xx (xx.x) | xx (xx.x) | xx (xx.x) |
| Fluocinolone acetonide (0.025%) | n (%) | xx (xx.x) | xx (xx.x) | xx (xx.x) | xx (xx.x) |
| Class 5: Lower Mid-Strength | | | | | |
| Fluticasone propionate (0.05%) | n(%) | vv (vv v) | vy (vy v) | vv (vv v) | vv (vv v) |
| Prednicarbate (0.1%) | n (%) | лл (лл.л) хх (хх х) | | $\mathbf{X} (\mathbf{X} \mathbf{X} \mathbf{X})$ | $\mathbf{x} \mathbf{x} (\mathbf{x} \mathbf{x} \mathbf{x})$ |
| Hydrocortisone probutate (0.1%) | $n(\frac{1}{2})$ | $\mathbf{x} \mathbf{x} (\mathbf{x} \mathbf{x} \mathbf{x})$ | $\mathbf{X} (\mathbf{X} \mathbf{X})$ | $\mathbf{X} (\mathbf{X} \mathbf{X}, \mathbf{X})$ | лл (лл.л) xx (xx x) |
| Triamainalana agatanida (0.1%) | n(70) | | | лл (лл.л) хх (хх х) | лл (лл.л) хх (хх х) |
| Eluccinalana acetanida (0.0259/) | n(70) | XX (XX.X) | XX (XX.X) | XX (XX.X) | XX (XX.X) |
| Fluoeinoione acetonide (0.025%) | II (70) | XX (XX.X) | XX (XX.X) | XX (XX.X) | XX (XX.X) |
| Class 6: Mild | | | | | |
| Alclometasone dipropionate (0.05%) | n (%) | xx (xx.x) | xx (xx.x) | xx (xx.x) | xx (xx.x) |
| Desonide (0.05%) | n (%) | xx (xx.x) | xx (xx.x) | xx (xx.x) | xx (xx.x) |
| Triamcinolone acetonide (0.025%) | n (%) | xx (xx.x) | xx (xx.x) | xx (xx.x) | xx (xx.x) |
| Hydrocortisone butyrate (0.1%) | n (%) | xx (xx.x) | xx (xx.x) | xx (xx.x) | xx (xx.x) |
| Fluocinolone acetonide (0.01%) | n (%) | xx (xx.x) | xx (xx.x) | xx (xx.x) | xx (xx.x) |
| Class 7: Losst Dotont | | | | | |
| Hydrocortisone (20//2 50/) | n(0/) | VV (VV V) | | vv (vv v) | VV (VV V) |
| Hydrocontisone (2.76/2.576) | (70) | XX (XX.X) | | XX (XX.X) | XX (XX.X) |
| nyurocorusone (0.5 to 0.1%) | Π (%) | XX (XX.X) | XX (XX.X) | XX (XX.X) | XX (XX.X) |
| Other [3] | n (%) | xx (xx.x) | xx (xx.x) | xx (xx.x) | xx (xx.x) |

[1] Percentage and all subsequent percentages based on the number treated.

[2] Subjects will be counted once per Rescue Medication term.

[3] Rescue medications reported as "Other" in the ERT will be cross referenced with allowed rescue medications, prohibited medications, and concomitant medications (e.g., emollients, antihistamines, etc.) and only "Other" resuce medications that are on the allowed rescue medication list are included here.

Source: Listing XXXX

PROGRAM NAME: XXXXXXXXXX

| | | B244 O.D. 5.0 | B244 O.D. 20.0 | Pooled B244 | Vehicle |
|-----------------------|----------------|---------------|-----------------------|--------------|--------------|
| Visit [1,2] | Statistic | (N=xx) | (N=xx) | (N=xx) | (N=xx) |
| Baseline | n | XX | XX | XX | XX |
| | Mean (SD) | xx.x (xx.xx) | xx.x (xx.xx) | xx.x (xx.xx) | xx.x (xx.xx) |
| | Median | XX.X | XX.X | XX.X | XX.X |
| | Min, Max | XX, XX | XX, XX | XX, XX | XX, XX |
| | | | | | |
| Weeks 1 – 2 | n | XX | XX | XX | XX |
| | Mean (SD) | xx.x (xx.xx) | xx.x (xx.xx) | xx.x (xx.xx) | xx.x (xx.xx) |
| | Median | XX.X | XX.X | XX.X | XX.X |
| | Min, Max | XX, XX | XX, XX | XX, XX | XX, XX |
| | | | | | |
| Weeks $1 - 2$ CFB [3] | n Mara (CD) | XX | XX | XX | XX |
| | Mean (SD) | XX.X (XX.XX) | XX.X (XX.XX) | XX.X (XX.XX) | XX.X (XX.XX) |
| | Median | XX.X | XX.X | XX.X | XX.X |
| | Min, Max | XX, XX | XX, XX | XX, XX | XX, XX |
| Weeks $3-4$ | n | XX | XX | xx | xx |
| | Mean (SD) | xx x (xx xx) | xx x (xx xx) | xx x (xx xx) | xx x (xx xx) |
| | Median | XX X | XX X | XX X | XX X |
| | Min Max | XX XX | XX XX | XX XX | XX XX |
| | , | , | , | , | , |
| Weeks 3 – 4 CFB | n | XX | XX | XX | XX |
| | Mean (SD) | xx.x (xx.xx) | xx.x (xx.xx) | xx.x (xx.xx) | xx.x (xx.xx) |
| | Median | XX.X | XX.X | XX.X | XX.X |
| | Min, Max | XX, XX | XX, XX | XX, XX | XX, XX |
| | | | | | |
| Weeks 1 – 4 Total | n | XX | XX | XX | XX |
| | Mean (SD) | xx.x (xx.xx) | xx.x (xx.xx) | xx.x (xx.xx) | xx.x (xx.xx) |
| | Median | XX.X | XX.X | XX.X | XX.X |
| | Mın, Max | XX, XX | XX, XX | XX, XX | XX, XX |
| Weeks 5 – 6 | n | XX | XX | XX | XX |
| Weeks 5 0 | Mean (SD) | xx x (xx xx) | xx x (xx xx) | xx x (xx xx) | xx x (xx xx) |
| | Median | XX X | XX X | XX X | XX X |
| | Min Max | XX XX | XX XX | XX XX | XX XX |
| | with, with | лл, лл | AA , AA | лл, лл | ΛΛ, ΛΛ |
| Weeks 5 – 6 CFB | n | XX | XX | XX | XX |
| | Mean (SD) | xx.x (xx.xx) | xx.x (xx.xx) | xx.x (xx.xx) | xx.x (xx.xx) |
| | Median | XX.X | XX.X | XX.X | XX.X |
| | Min, Max | XX, XX | XX, XX | XX, XX | XX, XX |

Table 14.3.9.1 Summary of Values and Change from Baseline for Rescue Medication Days for All Subjects (Safety Population)

| Weeks 7 – 8 | n Mean (SD) | xx xx.x (xx.xx) | xx xx.x (xx.xx) | xx xx.x (xx.xx) | xx xx.x (xx.xx) |
|-------------------|----------------|--------------------|--------------------|--------------------|--------------------|
| | Median | XX.X | XX.X | XX.X | XX.X |
| | Min, Max | XX, XX | xx, xx | XX, XX | XX, XX |
| Weeks 7 – 8 CFB | n | XX | XX | XX | XX |
| | Mean (SD) | xx.x (xx.xx) | xx.x (xx.xx) | xx.x (xx.xx) | xx.x (xx.xx) |
| | Median | XX.X | XX.X | XX.X | XX.X |
| | Min, Max | XX, XX | XX, XX | XX, XX | XX, XX |
| Weeks 5 – 8 Total | n | XX | XX | XX | XX |
| | Mean (SD) | xx.x (xx.xx) | xx.x (xx.xx) | xx.x (xx.xx) | xx.x (xx.xx) |
| | Median | XX.X | XX.X | XX.X | XX.X |
| | Min. Max | XX, XX | XX, XX | XX, XX | XX. XX |

[1] Baseline rescue medication days = number of rescue medication days from Day -14 to Day -1.

Weeks 1 - 2 rescue medication days = number of rescue medication days from Day 1 to Day of Visit 3 - 1.

Weeks 3 - 4 rescue medication days = number of rescue medication days from Day of Visit 3 to Day of Visit 4 - 1.

Weeks 1 - 4 total rescue medication days = number of rescue medication days from Day 1 to Day of Visit 4 - 1.

Weeks 5 - 6 rescue medication days = number of rescue medication days from Day of Visit 4 to Day of Visit 4 + 13.

Weeks 7 - 8 rescue medication days = number of rescue medication days from Day of Visit 4 + 14 to Day of Visit 5 - 1.

Weeks 5 - 8 total rescue medication days = number of rescue medication days from Day of Visit 4 to Day of Visit 5 - 1.

[2] Each time interval is normalized as a rate where (# Rescue Medication Days) = [(# Days Rescue Medications Used in Interval) / (# Actual Days in Interval)] * (# Expected Days in Interval).

[3] CFB = Change from Baseline.

Source: Listing XXXX PROGRAM NAME: XXXXXXXXX

| | | B244 O.D. 5.0 | B244 O.D. 20.0 | Pooled B244 | Vehicle |
|---------------------|----------------------|----------------------|----------------------|--|----------------------|
| Visit [1,2] | Statistic [4] | (N=xx) | (N=xx) | (N=xx) | (N=xx) |
| Baseline | n/N (%) | xx/xx (xx.x) | xx/xx (xx.x) | xx/xx (xx.x) | xx/xx (xx.x) |
| | Mean (SD) | xx.x (xx.xx) | xx.x (xx.xx) | xx.x (xx.xx) | xx.x (xx.xx) |
| | Median | XX.X | XX.X | XX.X | XX.X |
| | Min, Max | XX, XX | XX, XX | XX, XX | XX, XX |
| Washer 1 2 | m/NI(0/) | / () | | | |
| weeks $1-2$ | n/N(%) | XX/XX (XX.X) | XX/XX (XX.X) | XX/XX (XX.X) | XX/XX (XX.X) |
| | Median | XX.X (XX.XX) | XX.X (XX.XX) | XX.X (XX.XX) | XX.X (XX.XX) |
| | Median | XX.X | XX.X | XX.X | XX.X |
| | Min, Max | XX, XX | XX, XX | XX, XX | XX, XX |
| Weeks 1 – 2 CFB [3] | Ν | XX | XX | XX | XX |
| LJ | Mean (SD) | xx.x (xx.xx) | xx.x (xx.xx) | xx.x (xx.xx) | xx.x (xx.xx) |
| | Median | XX.X | XX.X | XX.X | XX.X |
| | Min, Max | XX, XX | XX, XX | XX, XX | XX, XX |
| | | | | | |
| Weeks $3 - 4$ | n/N (%) | xx/xx (xx.x) | xx/xx (xx.x) | xx/xx (xx.x) | xx/xx (xx.x) |
| | Mean (SD) | xx.x (xx.xx) | xx.x (xx.xx) | xx.x (xx.xx) | xx.x (xx.xx) |
| | Median | XX.X | XX.X | XX.X | XX.X |
| | Min, Max | XX, XX | XX, XX | XX, XX | XX, XX |
| Weeks 3 – 4 CFB | Ν | XX | XX | XX | XX |
| | Mean (SD) | xx.x (xx.xx) | xx.x (xx.xx) | xx.x (xx.xx) | XX.X (XX.XX) |
| | Median | XX.X | XX.X | XX.X | XX.X |
| | Min, Max | XX, XX | XX, XX | XX, XX | XX, XX |
| Wests 1 4 Tetel | $\sim D I (0/)$ | | | | |
| weeks 1 – 4 Total | n/N (%) Maar (SD) | XX/XX (XX.X) | XX/XX (XX.X) | XX/XX (XX.X) | XX/XX (XX.X) |
| | Mean (SD) | XX.X (XX.XX) | XX.X (XX.XX) | XX.X (XX.XX) | XX.X (XX.XX) |
| | Median | XX.X | XX.X | XX.X | XX.X |
| | Min, Max | XX, XX | XX, XX | XX, XX | XX, XX |
| Weeks 5 – 6 | n/N (%) | xx/xx (xx.x) | xx/xx (xx.x) | xx/xx (xx.x) | xx/xx (xx.x) |
| | Mean (SD) | xx.x (xx.xx) | XX.X (XX.XX) | xx.x (xx.xx) | xx.x (xx.xx) |
| | Median | XX.X | XX.X | XX.X | XX.X |
| | Min, Max | XX, XX | XX, XX | XX, XX | XX, XX |
| Weeks 5 – 6 CFB | Ν | vv | vv | vv | vv |
| WCCKS J = 0 CI D | Mean (SD) | ал ху х (ух хх) | лл ху х (ух хх) | лл хх х (хх хх) | лл хх х (хх хх) |
| | Median | лл.л (лл.лл) хх х | лл.л (лл.лл) хх х | лл.л (лл.лл) хх х | лл.л (лл.лл) УУ У |
| | Min May | ~~~~ VV VV | АЛ.Л УУ УУ | ~~~~~~~~~~~~~~~~~~~~~~~~~~~~~~~~~~~~~~ | 77.7 VV VV |
| | IVIIII, IVIAN | λλ, λλ | лл, лл | λλ, λλ | λλ, λλ |

Table 14.3.9.2 Summary of Values and Change from Baseline for Rescue Medication Days for Subjects Who Took At Least One Rescue Medication (Safety Population)

| Weeks 7 – 8 | n/N (%) Mean (SD) | xx/xx (xx.x) xx.x (xx.xx) | xx/xx (xx.x) xx.x (xx.xx) | xx/xx (xx.x) xx.x (xx.xx) | xx/xx (xx.x) xx.x (xx.xx) |
|-------------------|----------------------|------------------------------|------------------------------|------------------------------|------------------------------|
| | Median | XX.X | XX.X | XX.X | XX.X |
| | Min, Max | XX, XX | XX, XX | XX, XX | XX, XX |
| Weeks 7 – 8 CFB | Ν | XX | XX | XX | XX |
| | Mean (SD) | xx.x (xx.xx) | xx.x (xx.xx) | xx.x (xx.xx) | xx.x (xx.xx) |
| | Median | XX.X | XX.X | XX.X | XX.X |
| | Min, Max | XX, XX | XX, XX | XX, XX | XX, XX |
| Weeks 5 – 8 Total | n/N (%) | xx/xx (xx.x) | xx/xx (xx.x) | xx/xx (xx.x) | xx/xx (xx.x) |
| | Mean (SD) | xx.x (xx.xx) | xx.x (xx.xx) | xx.x (xx.xx) | xx.x (xx.xx) |
| | Median | XX.X | XX.X | XX.X | XX.X |
| | Min. Max | XX. XX | XX. XX | XX. XX | XX, XX |

[1] Baseline rescue medication days = number of rescue medication days from Day -14 to Day -1.

Weeks 1 - 2 rescue medication days = number of rescue medication days from Day 1 to Day of Visit 3 - 1.

Weeks 3 - 4 rescue medication days = number of rescue medication days from Day of Visit 3 to Day of Visit 4 - 1.

Weeks 1 - 4 total rescue medication days = number of rescue medication days from Day 1 to Day of Visit 4 - 1.

Weeks 5 - 6 rescue medication days = number of rescue medication days from Day of Visit 4 to Day of Visit 4 + 13.

Weeks 7 - 8 rescue medication days = number of rescue medication days from Day of Visit 4 + 14 to Day of Visit 5 - 1.

Weeks 5-8 total rescue medication days = number of rescue medication days from Day of Visit 4 to Day of Visit 5-1.

[2] Each time interval is normalized as a rate where (# Rescue Medication Days) = [(# Days Rescue Medications Used in Interval) / (# Actual Days in Interval)] * (# Expected Days in Interval).

[3] CFB = Change from Baseline.

[4] n = Number of subjects who have taken at least one rescue medication during that time point. N = Number of subjects with data at that time point. Statistics for Mean, SD,

Median, Min, and Max are computed for subjects who have taken at least one rescue medication during that time point.

Source: Listing XXXX PROGRAM NAME: XXXXXXXXX

Table 14.3.10 Summary of Medical History by System Organ Class and Preferred Term (Safety Population)

| | | B244 O.D. 5.0 | B244 O.D. 20.0 | Pooled B244 | Vehicle |
|---|-----------|---------------|----------------|-------------|-----------|
| | Statistic | (N=xx) | (N=xx) | (N=xx) | (N=xx) |
| Number of Subjects with at Least One MH Event [1] | n (%) | xx (xx.x) | xx (xx.x) | xx (xx.x) | xx (xx.x) |
| System Organ Class #1 [2,3] | n (%) | xx (xx.x) | xx (xx.x) | xx (xx.x) | xx (xx.x) |
| Preferred Term #1 | n (%) | xx (xx.x) | xx (xx.x) | xx (xx.x) | xx (xx.x) |
| Preferred Term #2 | n (%) | xx (xx.x) | xx (xx.x) | xx (xx.x) | xx (xx.x) |
| Preferred Term #3 | n (%) | xx (xx.x) | xx (xx.x) | xx (xx.x) | xx (xx.x) |
| etc. | | | | | |
| System Organ Class #2 | n (%) | xx (xx.x) | xx (xx.x) | xx (xx.x) | xx (xx.x) |
| Preferred Term #1 | n (%) | xx (xx.x) | xx (xx.x) | xx (xx.x) | xx (xx.x) |
| Preferred Term #2 | n (%) | xx (xx.x) | xx (xx.x) | xx (xx.x) | xx (xx.x) |
| Preferred Term #3 | n (%) | xx (xx.x) | xx (xx.x) | xx (xx.x) | xx (xx.x) |
| etc. | | | | | |

[1] Percentage and all subsequent percentages based on the number treated.
[2] Subjects will be counted once per System Organ Class/Preferred Term.
[3] MedDRA Dictionary version XX.X was used to code medical history events.
Source: Listing XXXX
PROGRAM NAME: XXXXXXXXX

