The day of first dose of study medication is Day 0 in the Schedule of Assessments (SOA) per protocol but will be considered relative study Day 1 in the SAP in order to construct Clinical Data Interchange Standards Consortium (CDISC) compliant datasets.

The Baseline visit (Day 0 per protocol) will take place once the results of Screening assessments are obtained, suggesting that the subject is eligible for entering the study. During this visit, those subjects who qualify for entering the study will be randomized to one of the study arms in a ratio of 1:1:1.

For all safety analyses, Baseline will be defined as the most recent measurement prior to the first administration of study drug.

The patient reported local tolerability diary for the first 7 days of treatment will be reported as relative study Day 1 to Day 7 in the eDiary, which corresponds to Day 0 to Day 6 per protocol. For the patient reported local tolerability diary, the first measurement occurs at the end of the first day of treatment (Day 0 Baseline visit per protocol, equivalent to relative study Day 1 reported in the patient reported local tolerability diary) and solicits subjects to record any changes in local tolerability symptoms compared to the previous day prior to treatment. Relative study Day 2 to Day 7 patient reported local tolerability diary entries (Day 1 to Day 6 per protocol) solicit subjects to record any changes in local tolerability symptoms compared to the previous day of treatment.

For all efficacy analysis derived from patient reported daily diary entries (e.g., WI-NRS, AI-NRS), Baseline period is defined as the average of the 1-week period before randomization (Day

STATISTICAL ANALYSIS PLAN

Version 3.0 12-Jan-22

-7 to -1) where the subject is observed for their medical condition (see also Section 6.5.3). For the primary analysis, at least 1 day of daily diary entry is required to calculate the Baseline WI-NRS and AI-NRS. For the sensitivity analysis, at least 4 days of daily diary entries are required.

Baseline WI-NRS = (Sum of daily WI-NRS scores from Day -7 to Day -1) / (Total number of WI-NRS diaries entered from Day -7 to Day -1)

Baseline AI-NRS = (Sum of daily AI-NRS scores from Day -7 to Day -1) / (Total number of AI-NRS diaries entered from Day -7 to Day -1)

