7.5.5 Patient Reported Local Tolerability

Patient Reported Local Tolerability assesses the following local tolerability symptoms: skin redness and/or color change, itching, burning and/or stinging, pain and/or tenderness, and new or changing rash. Responses are provided according to the following scale:

0 = None 1 = Mild 2 = Moderate 3 = Severe

Each of the 5 questions for local skin tolerability will be summarized by day and treatment as categorical variable (grade) by day and as continuous variable using the score. Patient reported local tolerability will be reported from Day 1 to 7 and in shift tables. Day 1 is the first day of treatment in relation to the previous untreated day and the change in tolerability for subsequent days (Day 2 to Day 7) is in relation to the previous treated day.

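### On SAP 6.4's definition, the change-from-previous-day rows in Table 14.3.6.1 difference scores that are already changes, and the reference day must be reconciled with Protocol Appendix G

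*SAP*

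**What the plan says.** **Reference day.** SAP 6.4 says the Day 1 entry records change "compared to the previous day prior to treatment", and that Day 2 to 7 entries "solicit subjects to record any changes in local tolerability symptoms compared to the previous day of treatment". SAP 7.5.5 is consistent but less explicit: "the change in tolerability for subsequent days (Day 2 to Day 7) is in relation to the previous treated day".

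**Scale.** Protocol 11.4 says the eDiary uses the Appendix G questions. Appendix G asks subjects to grade the changes they observed, on a 0 to 3 scale for five symptoms, and names no reference day. Grade 0 means nothing new or increased, and no grade records improvement.

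**Displays.** SAP 7.5.5 says each question will be "summarized by day and treatment as categorical variable (grade) by day" and also as a continuous score, for Days 1 to 7, with shift tables. The safety table list has two local tolerability tables:

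- Table 14.3.6.1, "Summary of Values and Change from Previous Day for Patient Reported Local Tolerability (Safety Population", gives n, mean (SD), median and range for each day's score and adds a CFPD block from Day 2. Its only definitional footnote is "CFPD = Change from Previous Day".
- Table 14.3.6.2, "Shift from Previous Day for Patient Reported Local Tolerability (Safety Population", crosses each day's grade with the previous day's. Its only numbered footnote is "Percentage and all subsequent percentages based on the number treated".

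Listing 16.2.9 codes None as 0 without saying that it means nothing new.

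**The concern.** Change in local skin tolerability is a named safety endpoint (Protocol 4.2, SAP 3.2.4). If a Day 2 to 7 score is already a change since yesterday, today's score minus yesterday's compares two changes and is not the quantity in the label. A reader who takes the label at face value will see a negative CFPD, or a Moderate-to-None cell in the shift table, as recovery. Under the previous-day definition the diary cannot in general show recovery, and no footnote warns of this. Separately, a reader looking for the share of subjects at each grade on each day, which 7.5.5 leads one to expect, would have to rebuild it from the shift table.

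**Working it through.** The plan states no figure to reproduce here, and it gives no formula for CFPD. I take CFPD on day d as score(d) minus score(d-1), which the row layout implies.

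**1. All score pairs.** On a 0 to 3 scale there are 4 x 4 = 16 pairs (yesterday, today).

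- Pairs reporting worsening today (score 1 or more): 4 x 3 = 12. Of these, 6 give a CFPD of 0 or less: (1,1), (2,1), (2,2), (3,1), (3,2), (3,3).
- Pairs with a negative CFPD: 6. Three are nothing-new days, (1,0), (2,0), (3,0). Three report worsening, (2,1), (3,1), (3,2).

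**2. State-worded grades.** Appendix G has 5 x 3 = 15 non-zero grades. Grade 3 for redness, burning/stinging and pain describes a state rather than an increase, which leaves 15 - 3 = 12 change-worded grades. For those three symptoms, leaving grade 3 does show that the severe state ended, and 3 followed by 3 does mean that it continued. Setting grade 3 aside altogether leaves 3 x 3 = 9 pairs. Six of them report worsening today, and 3 of those 6, (1,1), (2,1) and (2,2), still give a CFPD of 0 or less.

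**3. Seven-day records under the two possible references.**

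| Course | Reference | Scores, Days 1-7 | CFPD, Days 2-7 |
|---|---|---|---|
| Grade 2 on Day 1, persists | previous day | 2,0,0,0,0,0,0 | -2,0,0,0,0,0 |
| Grade 2 on Day 1, resolves | previous day | 2,0,0,0,0,0,0 | -2,0,0,0,0,0 |
| Mild increase every day | previous day | 1,1,1,1,1,1,1 | 0,0,0,0,0,0 |
| Grade 2 on Day 1, persists | pre-treatment | 2,2,2,2,2,2,2 | 0,0,0,0,0,0 |
| Grade 2, gone from Day 3 | pre-treatment | 2,2,0,0,0,0,0 | 0,-2,0,0,0,0 |

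Under the previous-day reference, persistence and resolution look identical. Daily worsening has the same CFPD as no reaction, although the value row still shows 1. Under a pre-treatment reference CFPD behaves as its label says. The reference day therefore decides the matter.

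**4. Rebuilding grades from the shift table.** Row sums of Table 14.3.6.2 give Days 2 to 7, and its Day 2 columns give Day 1. The shell has no totals and no category for missing entries, so it counts only subjects with entries on both days. Let p be daily completion and r the correlation between the two days' entries being present. Then P(both) = p^2 + r x p(1-p), and the share of a day's entries lost is 1 - P(both)/p = (1-p)(1-r).

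The plan gives neither p nor r for treatment. I assume p = 0.80, 0.90 or 0.95 (0.80 is only the washout entry threshold in inclusion criterion 8) and 192 treated per arm, the number planned for randomization.

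| p | Entry that day | Both days, r = 0 | Lost, r = 0 | Lost, r = 0.5 |
|---|---|---|---|---|
| 0.80 | 153.6 | 122.9 | 20% | 10% |
| 0.90 | 172.8 | 155.5 | 10% | 5% |
| 0.95 | 182.4 | 173.3 | 5% | 2.5% |

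For r of 0 or more the loss is at most 1-p, and it approaches zero as gaps cluster fully within subjects.

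**The case against.** The strongest objection is that the fielded eDiary wording is not in these documents. The Appendix G questions name no reference day, so subjects may have compared with their skin before treatment. CFPD would then be meaningful and the shells could stand. In addition, the 7.5.5 sentence follows directly on the mention of shift tables and could be read as defining the derived change rather than the score. Both arguments stand as far as they go: only 6.4 is explicit, and the documents do not support deleting CFPD before the wording is checked. They do not rescue the plan as written, because under a pre-treatment reference 6.4 is wrong. The definition and the display cannot both hold.

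It can also be said that Appendix G itself defines grade 0 as nothing new, that SAP 7.5.2 describes the solicited symptoms as new ones, and that no SAP text reads a negative CFPD as recovery. That is true, so the gap is one of presentation. The tables are still read apart from those texts, and their footnotes do not carry the meaning over.

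Finally, the shift table does show grades by day, arm and symptom. A reader might infer that 7.5.5's categorical summary is missing altogether. It is not: it can be rebuilt in part, and the listing holds every rating. What is missing is a direct shell that covers all subjects with an entry that day.

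**Conclusion.** The point holds on SAP 6.4's definition, and it is minor. Taken with that definition, the CFPD rows difference a change, and a Moderate-to-None cell in Table 14.3.6.2 does not show recovery. The exception is that leaving a state-worded grade 3 shows that the severe state ended. The texts must be reconciled on the reference day whichever reference was fielded.

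A reader might infer that the local tolerability data are unusable or that the safety conclusions are at risk. The documents do not support that. The daily values stand, including the Day 1 contrast with untreated skin, as do the ratings in Listing 16.2.9. Adverse events follow a separate route through the investigator's judgement (SAP 7.5.2), and no test or decision rule uses CFPD.

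The conclusion assumes that CFPD is a simple difference of consecutive scores. The loss figures for rebuilding grades rest on assumed completion rates. With independent gaps they are an upper bound; positive clustering makes them smaller.

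**What to change.** 1. Check the eDiary wording as fielded, and reconcile SAP 6.4, SAP 7.5.5 and Appendix G on the reference day. This comes first because step 2 depends on it.
2. If the reference is the previous day, drop the CFPD rows from Table 14.3.6.1, retitle it as a summary of daily values, and document the dropped statistic. Keep Table 14.3.6.2, read as reported worsening on consecutive days. If the reference is pre-treatment skin, correct 6.4 and 7.5.5, and CFPD may stay.
3. In either case, footnote both tables and Listing 16.2.9 with the reference day, and state that 0/None means no new or increased symptom. Only if the previous-day reference applies, add that grades not worded as a state cannot show resolution.
4. Add n (%) per grade for each of Days 1 to 7, by arm and symptom, as 7.5.5 states.

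The cost is small and uses data already collected. Dropping CFPD removes 6 days x 5 symptoms x 4 statistic rows x 4 columns = 480 cells. The grade block adds 4 grades x 7 days x 5 symptoms x 4 columns = 560, a net increase of 80. SAP 6.3 allows format, layout and title changes without a revision. Correcting 6.4 or 7.5.5 would be a text change, and the dropped statistic should be documented.
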